6.3.3.5 Medications that are CYP2C8, CYP2C9 and CYP3A4/5 substrates with narrow therapeutic index

Ribociclib is a potent inhibitor of drugs metabolized by the cytochromes CYP2C8, CYP2C9 and CYP3A4/5 *in vitro*. Because of the potential risk for drug-drug interactions, using concomitant medications known to be metabolized by these enzymes and that have a low therapeutic index is not permitted in the study. Refer to [Appendix 2](#) for a list of these medications. Please note that this list may not be comprehensive. Patients should stop using medications at least 7 days prior to first dose of treatment.

6.3.3.6 Herbal medications

Herbal preparations/medications are not allowed throughout the study, as a potential drug-drug interaction is always possible. These herbal medications include, but are not limited to: Cannabis Oil, St. John's wort, Kava, ephedra (ma huang), gingko biloba, dehydroepiandrosterone (DHEA), yohimbe, saw palmetto, and ginseng.

Patients should stop using herbal medications at least 7 days prior to first dose of treatment.

6.3.3.7 Medications that may prolong the QT interval or have a known risk of inducing Torsades de Pointes

There is preclinical and clinical evidence that ribociclib can induce QTc prolongation. [REDACTED]

While events of QTc prolongation have been observed at the dose of 600 mg qd, none of these events have been clinically significant or associated with other cardiac abnormalities. QT changes become evident in the first cycle by Day 8 and later (once steady-state is reached), are associated with the maximum drug levels between 1 and 8 h post-dose, and remain stable or improve in subsequent cycles. All ribociclib protocols have strict eligibility criteria related to baseline cardiac status particularly related to arrhythmias and baseline increase in QT interval. Local ECG monitoring for changes in the QT interval are conducted at various time points. Criteria for stopping ribociclib treatment are provided if the QTcF is > 500 ms. Clear restarting guidelines are provided in all protocols.

In case of QT prolongation, analysis of serum potassium, calcium, phosphorus, and magnesium, should be performed and if values are below lower limit of normal, adequate corrective measures should be taken. In the case of a QTcF >500 ms, the ECG should be repeated and assessed by a physician to confirm the value. The mean value of three ECG collected at 2 min intervals should be used. Treatment with ribociclib should only be resumed once the reason for the QT prolongation (electrolyte abnormality, concomitant treatment etc.) has been identified and corrected, and the QTcF has returned below 500 ms.

The co-administration of medications that may increase the risk of QTc prolongation are prohibited in clinical trials with ribociclib. These include medications that may increase the exposure of ribociclib (e.g., strong CYP3A4 inhibitors; see 6.3.3.4) and medications that have a strong risk for QT prolongation. Medications that have a mild to moderate risk for QT prolongation should be used with caution. In case of QT prolongation, review of concomitant medication usage should be performed. A list associated with QT prolongation and Torsades de Pointes is available online at www.qtdrugs.org.

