Grade 4 (> 20.0 x ULN) without bilirubin elevation to > 2.0 x ULN	Discontinue study treatment.	Discontinue study treatment.
AST or ALT and concurrent Total Bilirubin		
For patients with normal ALT and AST and total bilirubin at baseline: AST or ALT >3.0 x ULN combined with total bilirubin > 2 x ULN without evidence of cholestasis Or	Discontinue study treatment.	Discontinue study treatment.

Worst toxicity (CTCAE 4.03 Grade)*	Regimen Modifications for Ribociclib Management Recommendations	Regimen Modifications for Everolimus Management Recommendations
For patient with elevated AST or ALT or total bilirubin at baseline: baseline: [AST or ALT >2 x baseline AND >3.0x ULN] OR [AST or ALT 8.0 x ULN]- whichever is lower- combined with [total bilirubin > 2 x baseline AND >2.0 x ULN]		
Confounding factors and/or alternative causes for increased transaminases should be excluded before dose interruption/reduction. They include but are not limited to: concomitant medications, herbal preparations or dietary supplements, infection, hepato-biliary disorder or obstruction, new or progressive liver metastasis, and alcohol intake.		

Worst toxicity (CTCAE 4.03 Grade)*	Regimen Modifications for Ribociclib Management Recommendations	Regimen Modifications for Everolimus Management Recommendations
QTcF Prolongation		
For all grades	
Check the quality of the ECG and the QT value and repeat if needed.
 
Perform analysis of serum electrolytes (K+, Ca++, Phos Mg++). If outside of normal range, interrupt ribociclib administration, correct with supplements or appropriate therapy as soon as possible, and repeat electrolytes until documented as normal.
 
Review concomitant medication usage for the potential to inhibit CYP3A4 and/or to prolong the QT interval.
 
Check compliance with correct dose and administration of ribociclib. (Consider collecting a time matched PK sample: record date/time of last study drug dose.)
	N/A
Grade 1 (QTc 450-480 ms)	Perform steps 1-4 as directed in "For All Grades." Continue regimen.	Continue regimen.

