Grade 2 (QTc 481-500 ms)	
Interrupt ribociclib. Perform steps 1-4 as directed in "For All Grades."
 
Perform a repeat ECG one hour after the first QTcF of ≥ 481 ms.
 
• If QTcF < 481 ms, restart ribociclib at the same dose. No dose adjustment required for first occurrence.• If QTcF remains ≥ 481 ms, repeat ECG as clinically indicated until the QTcF returns to < 481 ms. Ribociclib should be reduced by 1 dose level• If QTcF ≥ 481 ms recurs, ribociclib should again be reduced by 1 dose level. 
Repeat ECGs 7 days and 14 days after dose resumption (then as clinically indicated) for any patient who has therapy interrupted due to QTcF ≥ 481 ms.
	If ribociclib is interrupted/discontinued, everolimus should also be interrupted/discontinued. Resume everolimus at same dose level if ribociclib is resumed at same or lower dose level.

Worst toxicity (CTCAE 4.03 Grade)*	Regimen Modifications for Ribociclib Management Recommendations	Regimen Modifications for Everolimus Management Recommendations
Grade 3 (QTc \geq 501 ms on at least two separate ECGs)	
Interrupt ribociclib. Perform steps 1-4 as directed in "For All Grades."
 
Perform a repeat ECG within one hour of the first QTcF of \geq501 ms.
 
• If QTcF remains \geq501 ms, consult with a cardiologist (or qualified specialist) and repeat cardiac monitoring as indicated until the QTcF returns to $<$481 ms.• If QTcF returns to $<$481 ms, ribociclib should be reduced by 1 dose level (please refer to the dosing schedule table).• If QTcF remains \geq 481 ms after performing steps 1-4 as directed in "For All Grades," discontinue ribociclib. 
Repeat ECGs 7 days and 14 days after dose resumption for any patient who has therapy interrupted due to QTcF \geq501 ms.
 
If QTcF of \geq501 ms recurs, discontinue ribociclib
	If ribociclib is interrupted/discontinued, everolimus should also be interrupted/discontinued. Resume everolimus at same dose level if ribociclib is resumed at lower dose level.
Grade 4 (QT/QTc \geq 501 or $>$ 60 ms change from baseline and Torsades de pointes or polymorphic ventricular tachycardia, or signs/symptoms of serious arrhythmia, unexplained syncope)	
Discontinue ribociclib+everolimus. Perform steps 1-4 as directed in "For All Grades."
 
Obtain local cardiologist consultation (or qualified specialist) and repeat cardiac monitoring as indicated until the QTcF returns to $<$481 ms.
	

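### After a confirmed QTcF above 500 ms in Phase 2, Section 6.3.3.7 sets a looser ribociclib restart limit (<500 ms) than Table 11 (<481 ms), and its visible text does not cite that table

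*Combined protocol and SAP*

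**What the plan says.** Section 6.3.3.7, on medicines that may prolong QT, covers a QTcF above 500 ms. The ECG is repeated and confirmed by a physician, using the mean of three tracings. The restart rule begins "Treatment with ribociclib should only be resumed once the reason for the QT prolongation" and requires that the cause be found and corrected and that "the QTcF has returned below 500 ms". The section gives no restart dose. Its only visible pointer to other restart rules is general: "Clear restarting guidelines are provided in all protocols".

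Table 11 (under Section 6.2.3, for treatment after resection, so Phase 2) covers QTcF of 501 ms or more on at least two ECGs as Grade 3:

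- On return to below 481 ms, "ribociclib should be reduced by 1 dose level (please refer to the dosing schedule table".
- If QTcF stays at 481 or more "ms after performing steps 1-4 as directed in" the all-grades row, ribociclib is discontinued.
- If 501 ms or more recurs, ribociclib is discontinued.

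For Grade 2 (481-500 ms), Table 11 interrupts ribociclib. If the repeat ECG is below 481 ms, the site may "restart ribociclib at the same dose. No dose adjustment required for first occurrence".

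Section 6.2.1 holds dosing after grade 3 toxicity until grade 1 or below and says a dose reduction may be considered. Section 6.2.2 names Table 11 as the source for re-initiation.

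**The concern.** One protocol gives two numeric restart limits for the same cardiac event in the same patients. The looser one stands in the section a site would open when checking concomitant medicines after a QT finding, a check that Table 11 itself asks for. A site that read only 6.3.3.7 could restart ribociclib at, say, 490 ms, a value at which Table 11 interrupts the drug even when there has been no worse event. It could also restart at the full dose, because 6.3.3.7 says nothing about dose.

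Phase 2 is where this would most likely arise. Section 6.3.3.7 says QT changes appear from Day 8 of the first cycle, whereas Phase 0 dosing lasts five days. Every dose level above Level 0 uses ribociclib 600 mg (Table 7), a dose at which 6.3.3.7 reports QTc prolongation. Section 8.1.3 lists QT prolongation as an adverse event of special interest.

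**Working it through.** The plan states no figure to reproduce. The check sets the rules side by side.

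**1. Is it the same event?** The 6.3.3.7 trigger is QTcF >500 ms, confirmed on repeat. Table 11 Grade 3 is >=501 ms on at least two ECGs. In whole milliseconds, >500 and >=501 are the same set, so in Phase 2 both rules apply.

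**2. Restart limits**

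| Source | QTcF needed to resume | Dose on resuming |
|---|---|---|
| 6.3.3.7 | <500 ms, cause corrected | not stated |
| Table 11, Grade 3 | <481 ms | one ribociclib level lower |
| 6.2.1, grade 3 toxicities | grade 1 or below | reduction may be considered |

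Section 6.2.1 prints no millisecond value. Table 11 defines Grade 1 as 450-480 ms, so grade 1 or below means <=480 ms, the same whole-millisecond set as <481 ms.

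**3. Where the limits disagree.** Values that meet <500 but not <481 run from 481 to 499: 499 - 481 + 1 = 19 values. The Table 11 Grade 2 band, 481 to 500, holds 500 - 481 + 1 = 20 values. So 19/20 = 95% of the Grade 2 band meets the 6.3.3.7 limit; only 500 ms does not.

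**4. What each text says at 490 ms after a Grade 3 event.** The QTcF condition in 6.3.3.7 is met. Table 11 does not allow a restart and orders discontinuation if the value persists after steps 1-4. Section 6.2.1 keeps dosing on hold, because 490 ms is Grade 2.

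**5. Ordering by severity.** A first Grade 2 event restarts only below 481 ms. Section 6.3.3.7 therefore states a looser limit for the worse event (500 ms) than Table 11 sets for the milder one (481 ms).

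**6. Dose.** The silence of 6.3.3.7 on dose is an omission. It does not contradict Table 11.

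**7. Patients affected.** Section 9.7.1 expects 3 to 12 Phase 2 patients. The visible documents give no rate of Grade 3 QTcF events, nor of patients then settling at 481-499 ms, so no expected number can be computed.

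**The case against.** The strongest reply is that the rules do not conflict. Section 6.3.3.7 states a necessary condition and does not give permission to restart. Table 11 adds a stricter condition, and a site that follows Table 11 breaches neither. Section 6.2.2 sends the reader to Table 11 for re-initiation, and 6.2.1 requires Sponsor discussion before any variance unless action is urgent. Section 6.3.3.7 also reads partly as general background on ribociclib trials. All of this is correct, and it limits the risk to a site that does not consult Table 11. Such a site, however, would not know that it was departing from the governing rule.

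Other points stand in part:

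- Section 6.2.1 is not independent support for 481 ms, since its millisecond value comes from Table 11's bands. Table 11 also departs from 6.2.1 elsewhere: Grade 3 neutropenia may resume at grade 2. The discrepancy rests on Table 11 itself, and 6.2.1 is only consistent with it.
- Part of 6.3.3.7 is blacked out, so the missing citation can be asserted only for the visible text. The two printed limits are not affected.
- The 19 values measure the width of the gap. They are not a count of patients or a measure of risk.
- Section 6.3.3.7 averages three ECGs while Table 11 refers to separate ECGs, so the measurements may not be identical. That would not account for limits of 500 and 481 ms.

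It can also be argued that this is merely editorial. But a printed cardiac restart limit that is met where the dose-modification table says hold or discontinue is a wrong threshold for Phase 2, which goes beyond a missing cross-reference.

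**Conclusion.** The concern holds. For a Phase 2 patient with a confirmed QTcF above 500 ms, 6.3.3.7 states a restart limit up to 19 ms looser (500 against 481 ms) than Table 11. Its visible text neither cites Table 11 nor mentions the dose reduction required there. It should be fixed, but its reach is small: it matters only if a site acts on 6.3.3.7 alone, and only among the 3 to 12 patients expected in Phase 2. The QT criterion for DLTs, the MTD and the handling of Grade 2 events are untouched. The conclusion assumes that Section 6.2 and Table 11 apply only after resection, as their titles say, and that the blacked-out part of 6.3.3.7 does not already direct the reader to Table 11.

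**What to change.** Keep the existing sentence in 6.3.3.7. It is the only visible restart condition for Phase 0, which Section 6.2 and Table 11 do not cover. Add directly after it:

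> In Phase 2, the Table 11 Grade 3 rule governs: resume only when the cause is corrected and QTcF is <481 ms, one ribociclib dose level lower (Table 10); discontinue if QTcF stays >=481 ms after steps 1-4 or if >=501 ms recurs.

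The cause-corrected condition carries over from 6.3.3.7 and is not in the Table 11 restart bullet. The linked everolimus hold and the ECGs at 7 and 14 days after resumption need no repeating, because the sentence makes Table 11 govern. Naming Table 10 also clarifies Table 11's unnumbered reference for the dose step.

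The cost is one sentence limited to Phase 2. Phase 0 rules, design, sample size and data collection do not change.

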6.4 Patient numbering, treatment assignment

6.4.1 Patient numbering

After the patient has signed the consent form, a unique screening (baseline) number will be assigned. This number is a 4-digit number starting with 0001. Once assigned, a baseline number cannot be reused for another patient.

6.4.2 Treatment assignment

Patient assignment to one of the three time-escalation cohorts in Phase 0 will rotate with 1 patient being placed into cohort 1, then 1 patient into cohort 2, and then 1 patient into cohort 3 and so on, whenever possible. Flexibility of assignment into the time cohorts within a dose level will be allowed, per Sponsor discretion, to assist with the scheduling of patients at the investigative site. For each dose level, three to six patients will be enrolled into the time interval cohorts, sequentially whenever possible (e.g. cohort 1, cohort 2, cohort 3, cohort 1...), with at least 1 patient in each of the time intervals. See Section 4.1.1.

6.4.3 Treatment blinding

This study is open-label; therefore, the patient, the investigator's site personnel and Sponsor-Investigator are not blinded to treatment. Drug identity (name, strength) is included in the label text; disclosure envelopes are not provided.

6.5 Study drug preparation and dispensation

6.5.1 Study drug packaging and labeling

Clinical supplies will be obtained commercially by the Sponsor-Investigator and/or site investigator(s).

6.5.2 Drug supply and storage

Ribociclib/everolimus must be received by designated personnel at the study site, handled and stored safely and properly, and kept in a secured location to which only the investigator and designated site personnel have access. Upon receipt, the study treatment should be stored according to the instructions specified on the product label(s).

6.5.3 Study drug compliance and accountability

Clinical supplies must be received by a designated person at the study site, handled and stored safely and properly, and kept in a secured location to which only the investigator and designated assistants have access. Clinical supplies are to be dispensed only in accordance with the protocol. The investigator is responsible for keeping accurate records of the clinical supplies received, the amount dispensed to and returned by the subjects/patients, and the amount remaining at the conclusion of the study. In accordance with Good Pharmacy Practices, gloves should always be worn by study personnel if directly handling tablets or capsules that are returned (i.e., when counting returns). At the end of the study, all clinical supplies including partial and empty containers must be destroyed per institutional policies.

6.5.3.1 Study drug compliance

During Phase 0 of the trial, patients will receive 5 consecutive doses of ribociclib+everolimus and their compliance measure will be assessed by the study research nurse and principal investigator at each patient visit and information provided by the patient and/or caregiver. The same will apply when patients enroll in the Phase 2 continuation trial where patients receive 21 consecutive daily doses (3 weeks on / 1 week off).

6.5.3.2 Study drug accountability

The study research nurse and principal investigator will maintain study drug accountability for the duration of the proposed study. Records of study medication used, dosages administered, and intervals between visits and the completion of the study should be captured in the Drug Accountability Form.

6.5.3.3 Handling of other study treatment

Clinical supplies should be kept in a secured location; storage conditions: according to the product label(s). The clinical supplies storage area at the site must be monitored by the site staff for temperature consistency with the acceptable storage temperature range specified in this protocol or in the product label attached to the protocol. Documentation of temperature monitoring should be maintained.

6.5.4 Disposal and destruction

The study drug supply can be destroyed at the institution or third party, as appropriate, if permitted by local regulations, policies and authorized by IBTC.

7 Visit schedule and assessments

7.1 Protocol flow and visit schedule

[Table 13](#) lists all of the assessments and indicates when they are performed. Each post-surgical Phase 2 treatment cycle in patients is 28 days (the 28 days cycle length is fixed regardless of whether the dose of ribociclib+everolimus is withheld). All visits are to be scheduled according to the appropriate number of calendar days from Cycle 1 Day 1 of ribociclib+everolimus drug administration post-surgery. A visit window of ± 1 in Cycle 1 Days 8, 15, 22 and ± 3 days in Cycle 2 onward is allowed. PK sampling on Day 4/5 post-dose will have ± 5 min window for 0.5hr and 1 hour samples and ± 15 min window for remaining samples (2, 4, 7h).

Note: If treatment with ribociclib+everolimus is withheld at any time during the post-surgical phase (Phase 2), all study visits, and safety assessments should continue according to the appropriate number of calendar days from Cycle 1 Day 1 as per the schedule of assessments.

Surveillance imaging will adhere to current clinical standards, which include MR imaging at a minimum of every 3 months for Grade III/IV recurrent gliomas.

Table 13 Visit evaluation schedule

	PHASE 0						PHASE 2				Survival Follow Up Call/Letter
	Screening/ Baseline	Enrollment	At Home	Pre-surgical assess-ment	Craniotomy for resection tumor resection	Phase 0	Cycle 1	Cycle 2	Subsequent cycles	End of study treat-ment (EoT)	
Visit Number	1	2	n/a	3	4	5	6-9	10-13	14, 15,...	Last	
Day of cycle	-28 to-1	Day 1	Day 2 & 3	Day 4	Cohort 1&2 Day 5 or Cohort 3 Day 6	Post-Operative Visit	Day of Cycle	Day of Cycle	Day of Cycle	Last	30 days after last dose
Obtain Informed Consent	X										~every 3 months after safety phone call
Collect archival tissue	X										
Patient history											
Inclusion/exclusion criteria	X	Day 1 pre									
Diagnosis and extent of cancer	X										
Demography	X										
Relevant medical history/current medical conditions	X										
Prior antineoplastic therapy (meds, surgery, radiation)	X										
Prior/concomitant medications	X					Continuous				X	
Surgical and Medical Procedures	X	X		X	X	Continuous					
Phone Call / Letter											~Q3 months ¹³
Safety assessments											
MRI of brain	X ¹					X (post-op)	MR imaging minimum every 3 months			last MRI obtained	
Response Assessment (RANO)	X ¹					X (post-op)	minimum every 3 months			X	
Physical examination	X ²					X	1	1	1	X	
Performance status (ECOG)	X	X				X	1	1	1	X	
Height	X ²										
Weight	X ²					X	1	1	1	X	
ECG (12-Lead)	X ²	X ^{2,4}		X ⁴	X ⁴	X	15 ⁵	1,15 ⁵	1 ^{5,6}	X	

Initial Version date: 10/16/2018

Revision date: 03/11/2019, 5/07/2019, 09/26/2019, 03/17/2020, 08/26/2024

	PHASE 0						PHASE 2					Survival Follow Up Call/Letter
	Screening/ Baseline	Enrollment	At Home	Pre- surgical assess- ment	Craniotomy for resection tumor resection	Phase 0 Follow - Up	Cycle 1 (28d)	Cycle 2 (28d)	Subsequent cycles (28d)	End of study treat- ment (EoT)	Safety Follow- up (phone)	
Visit Number	1	2	n/a	3	4	5	6-9	10-13	14, 15,...	Last		
Day of cycle	-28 to-1	Day 1	Day 2 & 3	Day 4	Cohort 1&2 Day 5 or Cohort 3 Day 6	Post- Operative Visit	Day of Cycle	Day of Cycle	Day of Cycle	Last	30 days after last dose	~every 3 months after safety phone call
Vital signs	X ²					X	1, 15	1, 15	1	X		
Adverse events			Continuous		first study drug administration up to 30 days after last dose of study treatment					X		
Laboratory assessments												
Hematology (CBC w/Diff)		X		X ⁷		X	15	1, 15	1	X		
Chemistry (CMP, Mg+, Phos)		X ²		X ⁷		X	15	1, 15	1	X		
eGFR ³		X ²		X ⁷								
Coagulation (PT/INR, PTT)		X ²		X ⁷								
Lipid panel		X ²								1 ⁸		
Urinalysis (dipstick) with microscopic analysis		X ²					15	1	1			
Pregnancy test (serum HCG) if applicable		X ²										
Pregnancy test (urine) if applicable						X	1	1	1	X		
Study Drug												
Drug administration		X ⁹	X ⁹	X ⁹	X ⁹		Daily Days 1-28 day cycle ¹⁰					
Review of Home Dosing Diary and Symptom Diary				X			1	1	1	X		
PK & Biomarker sample collections												
PK Blood Sampling		X		X ¹¹	X ¹¹		1, 8, 15, 22 10	1, 8, 15, 22 10				
Collection of PK CSF					X							
Collection of PK/PD Tumor tissue					X					X ¹²		
Biomarker blood collection		X ²										

1 | The most recent MRI scan available should be utilized.

	PHASE 0						PHASE 2					Survival Follow Up Call/Letter
	Screening/ Baseline	Enrollment	At Home	Pre-surgical assessment	Craniotomy for resection tumor resection	Phase 0	Cycle 1	Cycle 2	Subsequent cycles	End of study treatment (EoT)	Safety Follow-up (phone)	
Visit Number	1	2	n/a	3	4	5	6-9	10-13	14, 15,...	Last		
Day of cycle	-28 to-1	Day 1	Day 2 & 3	Day 4	Cohort 1&2 Day 5 or Cohort 3 Day 6	Post-Operative Visit	Day of Cycle	Day of Cycle	Day of Cycle	Last	30 days after last dose	~every 3 months after safety phone call
2	Screening assessment may be completed at Day 1 predose, if completed at screening, does not need to be repeated at Day 1 pre-dose except for ECG and ECOG. Results must be available to confirm eligibility prior to dosing.											
3	Estimated glomerular filtration rate (eGFR)											
4	ECG Day 1 Pre-dose, Day 1: 2-4 hrs post-dose, and pre-surgical assessment (can be completed on Day 4 or Day 5 (Cohort 1&2) / Day 6 (Cohort 3)).											
5	ECG Pre-dose and 2-4 hours post dose on C1D15, C2D15, C3D1, C6D1; C9D1; and every 3 rd cycle...											
6	ECG Pre-dose C2D1, C4D1, C5D1; C7D1, C8D1, C10D1, C11D1; and every 1st and 2nd cycle...											
7	Performed at pre-surgical assessment as per SOC on Day 4 (can be completed on Day 5 (Cohort 1&2) or Day 6 (Cohort 3)).											
8	Lipid panel performed every 4th cycle D1											
9	Study drugs are administered in the clinics on D1, D4 and D5. Patients may take medications at home on D2 and D3											
10	Trough blood sample is collected prior to the drug administration on that day. Study drugs are administered in the clinics on the clinic visit days 1, 8, 15, 22.											
11	Blood samples will be obtained on Day 4 (the day before the surgery for Cohorts 1 & 2; 2 days before surgery for Cohort 3) at pre-dosing (trough level), 0.5, 1, 2, 4, 7 hours post dose (\pm 5 min window for 0.5hr and 1hr; \pm 15min window for 2, 4, 7hr samples). A pre-dosing (trough level) blood sample will also be obtained on Day 5 and a sample will be collected intra-operatively. In Dose Level 4+ only, PK blood sampling will occur at the same timepoints (pre, 0.5, 1, 2, 4, 6, 8 and 24) but will be obtained on Day 5 (the day of surgery); the 24 hour sample will be obtained on Day 6.											
12	Only Patients that have a recurrence and undergo an additional surgery for tumor resection											
13	The start of follow up for long-term survival begins following completion of the Day 30 safety follow up call. Subjects will continue to be followed until death or withdrawal of consent for the collection and reporting of data or lost to follow-up for up to 5 years. Public records may be used to collect survival data, i.e., obituary notices and public database searches for survival information.											

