6.1.4.2 Additional Dosing Guidelines for Pharmacokinetic Sampling / ECG / Chemistry panel / Lipid Panel Collection

On days with PK, ECG sampling, chemistry panel and/or lipid panel sampling, the following additional guidelines should be followed:

- On a day when PK blood collection is scheduled at the clinic, patients must take study treatment in the clinic under the supervision of the Investigator or designee. On all other days, patients may take the study treatment at home.
- On a day of chemistry panel and/or lipid panel sampling, patients should be fasting from food and drink for at least 8 hours overnight; however, it will not be considered a deviation if the patient is not fasting. Water is allowed during all fasting periods; however, coffee, tea and juice are not permitted during the fasting period. Patients must also take study treatment in the clinic under the supervision of the Investigator or designee. On all other days, patients may take the study treatment at home.
- Pre-dose samples should be drawn prior to dosing. The sampling time of the PK samples and the dosing time must be precisely recorded in the CRF. Furthermore, the dosing date and time the study medication was taken on the day before the PK assessment must be precisely recorded in the CRF.
- Post-dose PK samples should be collected after dosing of the study treatment and precisely recorded in the CRF.
- If a pre-dose PK sample should be obtained, then the sample should be collected after the ECG and before dosing of the study treatment when possible; or allow approximately 30 minutes after the sample is drawn before obtaining the ECG.

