6.3 Concomitant medications

In general, the use of any concomitant medication/therapy deemed necessary for the care of the patient (e.g., anti-emetics, anti-diarrheal agents) is permitted, except when specifically prohibited. Anesthesia may use medications that would otherwise be prohibited when deemed clinically necessary, but if possible should be avoided.

The patient must be told to notify the investigational site about any new medications he/she takes after the start of the ribociclib+everolimus treatment. All medications, including herbal/natural medications (excluding ribociclib treatment and prior antineoplastic treatments and blood

transfusions), surgeries and procedures (including physical therapy) administered within 28 days prior to the first dose of administration of ribociclib treatment through 30 days after the last dose of treatment will be recorded. Medications include not only physician prescribed medications, but also all over-the counter (OTC) medications, herbal medications (prohibited, see [Section 6.3.3](#)), food or vitamin supplements, and blood transfusions.

For up to date information on prohibited medications please refer to the following websites:

- Medication with a known risk of prolonging the QT interval or inducing Torsades de Pointes (please refer to <http://www.acert.org/medical-pros/drug-lists/drug-lists.cfm>)
- Strong inhibitors or strong inducers of CYP3A4/5 (please refer to <http://medicine.iupui.edu/flockhart/table.htm> or <http://www.druginteractioninfo.org>)
- Medications with a low therapeutic index that are primarily metabolized by CYP3A4/5, CYP2C8 and/or CYP2C9 (please refer to <http://medicine.iupui.edu/flockhart/table.htm> or <http://www.druginteractioninfo.org>)

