8.1.3 Adverse events of special interest (AESI)

Based upon the currently available information from the pre-clinical studies, mechanism of action, pharmacological class effect, and clinical data for ribociclib and everolimus, defined AESIs to date are: Hepatotoxicity, QT prolongation and Interstitial Lung Disease, and Pneumonitis.

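### The only on-drug Phase 0 ECG after repeated dosing has no stated time relative to dose, so the QTcF dose-limiting toxicity may be read at trough

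*Combined protocol and SAP*

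**What the plan says.** **Why QT matters here.** Section 8.1.3 names the events of special interest as "Hepatotoxicity, QT prolongation and Interstitial Lung Disease, and Pneumonitis". Table 9 makes QTcF of 501 ms or more on at least two separate ECGs a DLT. Section 6.1.3 counts DLTs over the first 5 days in Phase 0 and the first 28-day cycle in Phase 2.

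**When the effect is expected.** Section 6.3.3.7 says "QT changes become evident in the first cycle by Day 8 and later (once steady-state is reached"), and that the changes are "associated with the maximum drug levels between 1 and 8 h post-dose, and remain stable or improve in subsequent cycles".

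**Phase 0 ECGs.** Table 13, footnote 4: "ECG Day 1 Pre-dose, Day 1: 2-4 hrs post-dose, and pre-surgical assessment (can be completed on Day 4 or Day 5 (Cohort 1&2"), with Day 6 as the alternative for Cohort 3. Section 7.1.1.11.4 asks for a Day 5 ECG only if none was taken on Day 4, so one pre-surgical ECG is required.

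**Order around PK sampling.** If a pre-dose PK sample is due, Section 6.1.4.2 says "then the sample should be collected after the ECG and before dosing of the study treatment when possible". The alternative is an ECG about half an hour after the draw.

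**Surgery.** Section 6.3 says "Anesthesia may use medications that would otherwise be prohibited when deemed clinically necessary", adding that such drugs are to be avoided if possible. Appendix 2, Table 16 lists propofol, sevoflurane and ondansetron as known QT risks.

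**Phase 2 ECGs.** Footnote 5: "ECG Pre-dose and 2-4 hours post dose on C1D15, C2D15, C3D1, C6D1; C9D1" and every third cycle after that. Footnote 6 makes the Day 1 ECGs of Cycle 2 and of the cycles in between pre-dose only.

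**The concern.** A threshold DLT can only be counted if the measurement is taken when the threshold might be crossed. The protocol states when it expects ribociclib to lengthen QT, but its Phase 0 schedule does not require a reading at those hours once the drug has accumulated. With 3 to 6 patients per level, Table 8 turns on single events: 0 of 3 with a DLT means escalate, 1 of 3 means enter at least 3 more, and 2 or more means stop. One QTcF event seen or not seen can change the step taken. The two-ECG rule adds to this, because a first reading below the threshold prompts no confirmatory ECG.

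There is also a handover issue. Cohorts 1 and 2 go to craniotomy 1-3 h and 7-9 h after the last dose, within or close to the stated hours, and the plan does not guarantee that a post-dose QTcF after repeated dosing is on file by then.

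**Working it through.** No sample size or power figure is involved. The check places each scheduled ECG against Section 6.3.3.7, which has two parts: 1-8 h post-dose, and Day 8 or later at steady state.

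**1. Phase 0 ECGs (Table 13 and footnote 4)**

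| ECG | Doses taken | Fixed at 1-8 h post-dose? |
|---|---|---|
| Screening | 0 | no |
| Day 1 pre-dose | 0 | no |
| Day 1, 2-4 h | 1 | yes |
| Pre-surgical (Day 4, or Day 5/6) | 3 to 5 | no time stated |
| Post-operative visit, 7-14 days after surgery | off drug | no |

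One reading is fixed in the hour window, after a single dose. The one on-drug reading after repeated dosing is untimed.

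**2. Where a compliant pre-surgical ECG can fall**

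- Day 4, Levels 0-3: a pre-dose PK sample is drawn (Section 7.1.1.11.3). The preferred order is ECG, sample, dose, so the ECG comes about 24 h after the Day 3 dose. The half-hour alternative does not by itself reach 1 h post-dose.
- Day 4, Levels 4-6: no PK sample is due, so no ordering applies and any time complies.
- Day 5, Cohorts 1 and 2: footnote 11 requires a pre-dose sample on Day 5, so the same preference applies. An ECG between the dose and craniotomy is also allowed and could be in the window.
- Day 6, Cohort 3, just before surgery: 23-25 h post-dose (Section 4.1.1), beyond 8 h.

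Trough readings are therefore permitted in every cohort and preferred in several settings. No setting requires a reading at 1-8 h.

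**3. The Day 8 part.** Phase 0 dosing ends on Day 5, so no on-drug Phase 0 ECG can satisfy it. How far short Day 4 falls depends on the half-life, which the readable text does not give. Assume 24, 36 or 48 h with simple accumulation. The fraction of steady state after four daily doses is 1 − 2^(−96/t½):

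- 24 h: 1 − 2^(−4) = 94%
- 36 h: 1 − 2^(−2.67) = 84%
- 48 h: 1 − 2^(−2) = 75%

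This is an illustration for exposure only, not for QTcF.

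**4. Phase 2, Cycles 1-12 (footnotes 5 and 6)**

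- Cycle 1: 2 readings (Day 15 pre-dose and 2-4 h).
- Cycle 2: 3 readings (Day 1 pre-dose; Day 15 pre-dose and 2-4 h).
- Cycles 3, 6, 9, 12: 2 readings each on Day 1, total 8.
- Cycles 4, 5, 7, 8, 10, 11: 1 reading each on Day 1, total 6.

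Total 2 + 3 + 8 + 6 = 19. Two readings, C1D15 and C2D15 at 2-4 h, meet both parts of the window. From Cycle 3 there are 8 + 6 = 14 readings: 4 at 2-4 h post-dose, 10 pre-dose, and none on Day 8 or later. Even at the +3-day visit limit, a Day 1 visit falls no later than Day 4.

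Under 21 days on and 7 off, the last ribociclib dose is on Day 21 and the next Day 1 is Day 29: (29 − 21) × 24 = 192 h nominally. The pre-dose reading is then after the rest week, and the 2-4 h reading follows one dose.

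**5. A conflict that affects step 4.** Section 6.1.4.1 gives 21 days followed by a rest week, while the Table 13 dosing row indicates daily dosing across Days 1-28. Under daily dosing throughout, Day 1 from Cycle 2 on would be an on-drug day and the step 4 criticism would not apply.

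**The case against.** The strongest reply is that Section 6.3.3.7 places the effect by Day 8 and later, so a 5-day regimen cannot show it in full wherever the ECG is put. That stands as a limit on what Phase 0 can detect. It does not justify leaving the only repeat-dose reading untimed.

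Second, the pre-dose order applies only when possible, has an alternative, and does not reach Day 4 at Levels 4-6. Cohort 3 has no escalation slots from Level 1 up, so the Day 6 case is confined to Level 0 and the time-cohort expansions. This stands too: trough is permitted and in places preferred, not required.

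Third, C1D15 at 2-4 h post-dose lies inside the Phase 2 DLT period, and Table 7, note a, lets Phase 2 DLTs lower the MTD/RP2D. Well-timed QTcF readings therefore do reach dose selection for patients who continue. However, Section 4.1.2 has Phase 0 escalation decided by Phase 0 DLTs alone unless the DSMB determines otherwise.

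Fourth, the statement that changes stay stable or improve in later cycles supports lighter monitoring from Cycle 3. That makes the Phase 2 point secondary.

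Fifth, Section 7.2.2 allows safety evaluations at any time on clinical judgment, and the DSMB Chair authorises each escalation. Neither requires the missing reading. Text is also blacked out just before the QT statements in Section 6.3.3.7, and a rationale for the timing may be there.

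Two stronger readings are tempting. A reader might infer that QTcF is measured outside the effect window throughout the trial; C1D15 and C2D15 contradict that. A reader might also infer that QT DLTs are undercounted by a known amount. The documents give no QTcF variance and no peak-to-trough difference, so no miss rate can be derived.

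**Conclusion.** The point holds for Phase 0 and should be corrected. Of the scheduled Phase 0 ECGs, one is fixed at 1-8 h post-dose, and it follows the first dose. The sole on-drug ECG after repeated dosing may be taken at about 24 h post-dose in full compliance, while a QTcF threshold contributes to the primary MTD endpoint. The claim is that the reading may be at trough, not that it is. Downward bias in the DLT count follows only if sites do take it there and QTcF is lower at trough, as Section 6.3.3.7 suggests. Five days of dosing may understate the effect in any case.

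The Phase 2 point is secondary: 0 of 14 cycle readings in Cycles 3-12 are at steady state, provided the 21-on/7-off schedule applies. The C1D15 and C2D15 readings are adequately timed.

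**What to change.** Reconcile footnote 4 and Section 6.1.4.2 with Section 6.3.3.7 by giving the existing pre-surgical ECG a stated post-dose time inside the protocol's own 1-8 h window. The 2-4 h window already used on Day 1 and C1D15 fits the Day 4 in-clinic dose. On Day 5 it would collide with Cohort 1 surgery at 1-3 h. State in Section 6.1.4.2 that the ECG-before-sample order does not apply to this ECG.

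Cost: no ECG is added. At Levels 0-3 the patient is already present on Day 4 for the 2 h and 4 h PK samples; at Levels 4-6 it means about a 2 h wait. There are two trade-offs. A Day 4 reading is further from surgery than the Day 5/6 option: one day before for Cohorts 1 and 2, two days for Cohort 3. At Levels 4-6 it also precedes the single everolimus dose on Day 5, although Section 6.1.5 predicts no significant everolimus effect on ribociclib metabolism.

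For Phase 2, reconcile footnotes 5 and 6, the Table 13 dosing row, and Sections 6.1.4.1 and 6.3.3.7, so that the dosing pattern is stated once and the reason for Day 1 ECGs from Cycle 3 is clear. This need not create Day 15 visits: apart from imaging at least every 3 months, Table 13 dates assessments only on Day 1 after Cycle 2, so moving ECGs to Day 15 would add a clinic visit.
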